In a two year randomized, pilot study, two exercise training regimens (IMT and Aerobic) will be evaluated as compared to a control group by studying their effect on clinical end points and correlating them with central effects on cardiac remodeling specifically focusing on indices of left ventricular systolic and diastolic function (LVEDV, LVESV, EF, LV mass, LV longitudinal strain e' and E/e). Given that prior studies have predominantly studied aerobic exercise and there is no data available on the effect of IMT on cardiac remodeling or the peripheral effects, this study will provide us the unique opportunity to study IMT to determine its efficacy compared to aerobic training and will also provide mechanistic insight to overall change in symptoms. We anticipate that insights from this work will facilitate clinical implementation of exercise training and potentially provide insight into the use IMT as a therapy in individuals with HF who cannot perform aerobic exercise.

Overall Study Protocol: 75 HF patients will be enrolled. HF diagnosis will depend on physician diagnosis⁶⁵⁻⁶⁸. As part of this protocol 15 control subject will undergo a comprehensive pre- and post- assessments that will include a battery of physical function evaluations (aerobic, strength, and questionnaire indices), quality of life (QoL), and echocardiography. At the conclusion of their initial assessments they will continue with usual clinical care and will be retest on the same battery of assessment 12 weeks later. 60 patients already taking part in the VA MERIT F0834-R will have the option to additionally enroll into this study which would require them after enrollment into the Exercise Therapy protocol to complete an echocardiogram at baseline as well as post-intervention. All other parts of their participation will occur as part of the Exercise Therapy trial.

Table 4: Outline of protocol (by visit) for Controls group

Initial Assessment	Visit 1	Informed consent and physical exam, physical functional assessment battery (aerobic, strength, 6MWT, Hand Grip, and questionnaires), and echocardiographic
Exercise Training	12 weeks	Care as usual
Post assessment	Visit 38	Post-exercise assessment battery will mirror visit 1

Table 5: Outline of protocol (by visit) for Intervention Group

At time of randomization from VA MERIT F0834-R visit 3 of that protocol	Initial Assessment	Visit 1	Informed consent and echocardiographic

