Project Time Line

Year I →→→→→	Year II →→→→→
Start Recruiting	Continue Recruiting
Start Assessments	Assessments
Start EX sessions	Exercise Sessions
	Manuscript Preparation

Year	Year 1		Year 2	
Time frame	0-6M	6-12M	12-18M	18-24M
Staffing	ES, RA, EX	ES, RA, EX	ES, RA, EX	ES, RA, EX
Enrollment	15	20	20	10
What will be happening	Setup/purchase supplies/recruitment/initial assessment /	Recruitment/assessments/interventions	Recruitment/Assessments/interventions	Recruitment/Assessments/interventions / manuscripts preparation

Study Team: Throughout the trial, [name] will meet regularly with co-investigators (4 times a year initially, and increasing to monthly when data analysis begins). Drs. [name], [name], [name], [name], [name], [name] all work in the VA or within close proximity and can presumably come to the VA campus for these meetings. However, phone teleconferencing will also be available for those who cannot participate in person. The skillsets and backgrounds of the investigators (as detailed in their biosketchs and the budget section) are extremely complementary and have contributed to a collegial and productive dynamic.

All study staff that will be working on this project are currently on staff at the VABHS. The echo sonographer, research assistant, and exercise physiologist will be an integral part of the team, they will coordinate recruitment, participant screening, enrollment, perform assessment visits, and follow ups. The current VABHS infrastructure through the Clinical Studies Unit (CSU) provide the ability for one exercise physiologist to perform the functional assessment while another performed the exercise trainings. This will allow this physiologist to remain blinded to the subject's intervention group thus eliminating tester bias.

Statistical Analysis: General considerations: This is a pilot study, described below are continuous outcome measures, primarily changes in function outcomes and gene expression and either continuous or categorical predictors. In all instances, outcome variables will be evaluated for violation of model assumptions and transformation of these variables will be considered as a remedy if needed. Analyses will generally be performed with an intent-to-treat approach, with sensitivity analyses performed to assess the role of drop-outs on the results.

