Sample Size and Power: With respect to superiority testing for mixed models in **aim 1**, power for an equivalent t-test will be used with sample sizes of 30 for the active treatment and 15 in the control group. This will result in the ability to detect a difference of 0.91 standard deviation [SD] units with 80% power, assuming an alpha level of 5%. For non-inferiority testing in aim 1, we propose a detectable difference of zero, with a lower boundary of 0.65 SD units, which provides 80% power using an alpha level of 5%⁷⁹.

In **aim 2**, a mixed linear regression model with 7 predictors would result in a detectable R^2 of 0.19 compared to a null model with 80% power, assuming alpha=5% and 75 subjects.

Study Data Management and Quality Control:

Prior to the initiation of the study, all investigators and research staff involved in clinical activities will meet to review study procedures and will complete all required trainings on data and patient privacy procedures. Documentation of any protocol breaches will be required. Each protocol violation will be evaluated by the PI and a determination made regarding the validity of any justification for the violation.

The study databases will be located at the VABHS. The clinical database with all research data will be stored on VA network drives and housed behind the VA firewall on VA owned and maintained servers, which are backed up on a regular schedule. All computers will have Kerberos passwords and come equipped with antivirus software. Data will not be stored on desktops or on non-VA servers. Study data will be coded with a unique study identifier for each participant and stored in a de-identified manner. A study data set without identifiable information will be used for all data analysis. Identifiable information will be collected for patient tracking and safety purposes, but will only be kept for as long as the study is active. De-identified clinical data will be stored separately from the participant's name, contact information, and real SSN. Access to the cross-walk file linking the participant's identifiers and their study data will be restricted to the project manager. This file will be destroyed according to CSP policy after the study ends. Study data will be retained and stored after the study ends according to federal and local VA regulations. Access to the study data is heavily restricted to

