individuals with approval from the PI to access the data. Individuals must be properly credentialed research staff and must be compliant with VA security trainings (i.e., Research Data Security, HIPAA and VA Privacy Training, Cyber-Security, and Good Clinical Practices).

Dissemination and/or Implementation Plan: The findings of this study will be of key interest in a variety of scientific and clinical venues. Abstracts and associated manuscripts will target the Echocardiography, HF, and exercise research communities. Initial presentations/publications will include orientation to cardiac remodeling effects with focus on the overall mechanism of exercise induced clinical benefits and the relative contribution of central and peripheral effects with the 2 training modalities. We will also report on the role of exercise training modalities and their impact on heart failure management, issues of likely interest to HF and cardiac rehabilitation physicians. [name] and her team of investigators will participate in related meetings, particularly the American Heart Association (AHA). Drs. [name], [name], and [name] already regularly participate in the AHA/ACC/AHA as part of their careers. Likewise, the investigators participate in the American College of Sports Medicine, the HF Society of America and other laudable venues as part of their careers. Dissemination of the data/conclusions from this study will flow from these preexisting patterns.

Limitations: The goal to recruit 75 systolic HF patients, inclusive of men, women, and minorities is an inherent challenge for a two year proposal. We are confident we can achieve this because of the significant and well-organized initiatives we established within the VABHS (as part of previous pilot studies) to identify suitable candidates. A related limitation is the potential attrition of patients over an extended training trial. Illness and/or life stresses can potentially exacerbate attrition. [name] developed considerable experience with these types of dynamics in HF-ACTION (a large training trial in which there was only 5% attrition), and he will work closely with the study team to maintain subjects' adherence. Financial incentives will be helpful, but it became clear in HF-ACTION that the PI was the most important factor in maintaining patient participation. Steps will also be implemented to sustain participation in the event of illness, accidents, or travel.

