- Orthopedic exercise limitation
- Women who are pregnant, breastfeeding, or likely to become pregnant within the next 6 months
- Psychiatric hospitalization within the last 3 months
- Chronic ETOH or drug dependency.
- Exclusion criteria: Patients who have very poor acoustic windows in whom it is deemed that even with the use of contrast adequate image acquisition will not be possible will be excluded after initial assessment

B. Sources of research materials

All information pertaining to this project (e.g., screening forms, questionnaire data, interviews, cardiopulmonary testing results) will be held in the strictest confidence, will be kept in locked files, and will be available only to individuals directly involved with the project. Under no circumstances will individually identifiable data be released to anyone without written consent of the participant. Results will be published as group findings only. Assessment and treatment results will be discussed with the participant only and will only be used for research purposes unless patient give clearance for information to be provided for their own clinical care.

C. Potential Risk - During Assessments: - Controls only functional testing for all other patients will be completed as part of the Exercise Therapy protocol.

- During exercise testing assessments, just as when taking part in any exercise there are inherent risks associated. However, all candidates will undergo a cardiopulmonary exercise stress (CPX) test as part of their enrollment to provide baseline exercise indices, but also to provide a means to screen for safety prior to exercise training. Patients' physicians will refer only patients they expect to be stable. , A physician , will examine all study candidates before CPX and will also supervise the exercise tests to maximize safety. All testing will be completed by ACLS trained staff and during the stress test the physician will work in combination with an exercise physiologist to insure patient safety.

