The VA Boston is a large cardiovascular clinical center, encompassing 3 campuses (Jamaica Plain, West Roxbury, and Brockton) and several community based outpatient clinics (CBOC), with a high volume of heart failure seen throughout these campus. The plan will be to recruit 45 patients in year one, and 30 patients during year two, for a total of 75 participants. Primary recruitment for this study will occur as part of the already funded research project VA Merit F0834-R entitled “Exercise Therapy to Reduce Heart Failure Symptoms; Sorting Mechanisms of Benefit” (Site-PI, [name]; PI, [name]). Additionally control subject will be recruited through heart failure clinic, echocardiogram clinic and flyers post.

Only individuals who provide written informed consent may participate. In accordance with informed consent and HIPAA regulations, written informed consent and HIPAA forms will be obtained from each participant after a thorough explanation of procedures by a project staff person and the opportunity for the participant to ask and receive answers to questions. Participants will be informed of the nature of the investigation, the types of assessments and treatment involved, the potential risks involved in participation and will be asked to sign an informed consent statement prior to participating in the proposed study. In addition, participants will receive an explanation of how their information will be handled including all parties involved, data management, and plans to publish data in group format without identifying information. The Institutional Review Board of VA Boston Healthcare System will approve the protocol, consent, and authorization forms. Participants will also be informed that they are free to withdraw from the study at any time without any consequences.

B. Protection Against Risk

We will carefully screen to identify individuals whose risk for potential adverse outcomes is elevated were they to participate in the proposed research. All participants will have a thorough review of their medical records prior to enrolling in the study by study staff and study physicians. To determine stability prior to beginning exercise all participants will have a physical exam performed by a study cardiologist, physician or nurse, complete an exercise stress test that will be administered by trained personnel and supervised by a cardiologist, physician, or nurse practitioner.

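### The timeline table enrols 65 patients against 75 everywhere else, and the correctly computed power figures hold only if all 75 (30/30/15) give complete echo pairs

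*Combined protocol and SAP*

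**What the plan says.** **Total.** Overall Study Protocol says "75 HF patients will be enrolled", made up of two sources: "As part of this protocol 15 control subject will undergo a comprehensive pre- and post- assessments", and "60 patients already taking part in the VA MERIT F0834-R will have the option to additionally enroll into this study". Study Population, Limitations and Human Subjects repeat 75, and the Aim 2 power statement also uses 75 subjects. Recruitment and Consent Procedures gives the yearly split: "The plan will be to recruit 45 patients in year one, and 30 patients during year two, for a total of 75 participants".

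**Schedule.** The Project Time Line table covers four half-years and reads "Enrollment 15 20 20 10".

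**Power.** Sample Size and Power says that "power for an equivalent t-test will be used with sample sizes of 30 for the active treatment and 15 in the control group", giving a detectable difference of 0.91 SD at 80% power and 5% alpha. For non-inferiority between the two training arms it gives a boundary of 0.65 SD, a true difference of zero, 80% power and 5% alpha. It does not mention loss.

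**Loss.** Limitations names attrition as a risk and refers to "a large training trial in which there was only 5% attrition". The last exclusion criterion under Human Subjects concerns "Patients who have very poor acoustic windows in whom it is deemed that even with the use of contrast" usable images cannot be obtained; these patients leave after the initial assessment. No rate is given for them.

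**The concern.** Two things do not fit together. First, the enrolment table and the recruitment text give different totals, so a reader cannot tell from the schedule how many patients the study is set up to enrol. Second, the power section treats all 75 as analysable. The Aim 1 outcomes are changes in echo measures, so a patient without a usable second study adds little or nothing to the comparison. The protocol itself foresees some such patients.

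At stake is whether the two 80% power statements describe the data the study can expect. This matters most for the non-inferiority claim, where the 0.65 SD boundary is matched to 30 per arm with nothing to spare.

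**Working it through.** **1. Enrolment totals**

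| Source | Year 1 | Year 2 | Total |
|---|---|---|---|
| Project Time Line table | 15 + 20 = 35 | 20 + 10 = 30 | 65 |
| Recruitment and Consent Procedures | 45 | 30 | 75 |
| Overall Study Protocol | – | – | 15 + 60 = 75 |

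Year two agrees. Year one differs by 10.

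**2. Reproducing the plan's power figures**

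Method: two-sample t-test, with noncentrality δ = d / √(1/n₁ + 1/n₂), df = n₁ + n₂ − 2, and power from the noncentral t distribution. The protocol does not state sidedness; the choices below are the ones that reproduce its figures.

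- Superiority, 30 against 15, two-sided 5%: δ = 0.91 / √(1/30 + 1/15) = 2.878, df = 43, critical t = 2.017. Power is 80.3%; the difference detectable at 80% is 0.906 SD. The plan says 0.91.
- Non-inferiority, 30 against 30, one-sided 5%, true difference 0: δ = 0.65 / √(1/30 + 1/30) = 2.517, df = 58, critical t = 1.672. Power is 80.0%; the margin at 80% is 0.650 SD. The plan says 0.65.

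Both figures are right at 30/30/15, with almost no slack. Losing one patient is enough to fall below 80%: superiority 79.8% at 29 against 15 or 78.4% at 30 against 14, and non-inferiority 79.4% at 30 against 29.

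**3. The same formulas with fewer complete pairs**

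Power is at 0.91 SD (superiority) and 0.65 SD (non-inferiority). The last two columns give the difference and margin at 80% power.

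| Complete pairs (IMT/aerobic/control) | Superiority power | Non-inferiority power | Detectable difference | Margin |
|---|---|---|---|---|
| 75, no loss: 30/30/15 | 80.3% | 80.0% | 0.91 SD | 0.65 SD |
| 75, 5% loss: 28.5/28.5/14.25 | 78.2% | 78.2% | 0.93 SD | 0.67 SD |
| 65, assumed 26/26/13 | 74.2% | 74.8% | 0.98 SD | 0.70 SD |
| 65, assumed 25/25/15 | 77.5% | 73.3% | 0.94 SD | 0.71 SD |
| 65, assumed 30/30/5 | 44.8% | 80.0% | 1.39 SD | 0.65 SD |

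The 5% row uses the exact expected count, 75 × 0.95 = 71.25. The nearest whole-patient set in 2:2:1 ratio, 28/28/14, is 70 patients, a loss of 5/75 = 6.7%; it gives 77.4% and 77.5%. The splits of 65 are assumptions, because the table does not divide enrolment by arm.

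**4. Possible offset from baseline adjustment**

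If the SD in the power section is that of the outcome, and baseline is adjusted for with correlation ρ to follow-up, the residual SD shrinks by √(1 − ρ²). At 26/26/13, assumed ρ of 0 / 0.3 / 0.5 / 0.7 gives superiority power of 74 / 78 / 85 / 96% and non-inferiority power of 75 / 78 / 85 / 94%. At 28/28/14, ρ of about 0.26 restores 80% for both tests; at 26/26/13, about 0.37 does.

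**The case against.** The total of 75 is stated consistently throughout the protocol, while 65 can be derived only from one staffing and timeline table whose year-two entries match the text. That looks like a local slip in the table. The recruitment sentence adds up, and so does the power calculation. The only attrition rate cited belongs to an earlier trial, and at that rate the shortfall is about two points. Patients who cannot be imaged even with contrast might be counted as screen failures outside the 75. The planned mixed model may adjust for baseline, which the t-test calculation ignores, and sensitivity analyses for drop-outs are planned. The study calls itself a pilot.

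Most of this stands, and it limits the point. A reader might infer that the trial really is a 65-patient trial, or that the stated detectable differences are wrong or will not be achieved. The documents do not support either: at 75 with no loss the figures hold, and the table does not outrank the other statements of the total. A reader might also infer that enrolment runs to month 24, leaving no time for the 12-week echocardiogram. The table shows only a six-month bin with 10 patients, and entry by about month 21 is compatible with it.

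What the objection does not remove is the contradiction itself and the missing loss allowance. The power section takes no credit for baseline adjustment, does not say whether its SD is of the outcome or of change, and gives no correlation. Drop-out sensitivity analyses examine bias and do not restore sample size. Pilot or not, the plan commits to explicit 80% power and a formal non-inferiority test.

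**Conclusion.** The point holds in two parts. The enrolment table (65) contradicts the recruitment text and every other statement of the total (75), and this must be reconciled; the documents alone do not settle it, though the weight of statements favours 75. Separately, the Aim 1 power figures are correctly computed but conditional on 30/30/15 complete echo pairs with no loss.

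The size depends on assumptions. With 75 enrolled and the 5% rate from the earlier trial, both powers fall to about 78%, a modest shortfall. If 65 were the real target, the tests would drop to about 74–75% under a proportional split, and other splits move the loss between them: 30/30/5 leaves non-inferiority at 80% but takes superiority to about 45%. All of these use the protocol's unadjusted t-test. Baseline adjustment could offset some or all of the smaller losses, but that cannot be established without a stated correlation.

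**What to change.** 1. Correct the Project Time Line table or the recruitment text so that both give the same yearly figures and the same total.

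2. Restate Sample Size and Power for the expected number of evaluable echo pairs. For example: *75 enrolled, about 71 evaluable at an assumed 5% loss; about 78% power at 0.91 SD (superiority) and at 0.65 SD (non-inferiority), or 0.93 SD and 0.67 SD at 80% power.* If 65 is the real target, give the 65-patient figures with the actual split by arm.

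3. If the sponsor wishes to rely on baseline adjustment to hold 80%, state the assumed correlation and say which SD is meant.

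The cost is a change of wording and slightly less favourable stated figures. Restating the power does not require more patients.

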TIRE IMT will be administered progressively 40% week 1, 50% week 2, 60% the remainder of the protocol of the Maximal Inspiratory Pressure (MIP) and SMIP using a visual target that the patient watches on a monitor during the training. The visual target has been observed to facilitate inspiratory performance via biofeedback while the IMT progresses in respect to the work to rest ratio, with rest periods decreasing from 60 seconds at level A to 45, 30, 15, 10 and 10 seconds at levels B through F, respectively. TIRE IMT is characterized by through-range IMT with the need for patients to match or exceed 90% of the desired percentage of the on-screen target throughout the entire inspiratory effort (from RV to TLC). Thus, the training session continues until task failure indicated by an inability to match 90% of the on screen target, or until a maximum of 36 resisted breaths have been performed with an average duration of 25 minutes^{43,46}. Adherence and performance during TIRE training is captured automatically via TIRE computer software and each session is automatically performed at the desired workload (40% of MIP). An additional 20 minutes of IMT will be completed using the Threshold IMT. Threshold IMT will also be administered at progressively (40%, 50%, 60%) of MIP which will be adjusted each week to maintain a workload at 60% of MIP. Threshold IMT will require subjects to breathe through the mouthpiece of the Threshold device at a comfortable rate using diaphragmatic breathing techniques.

While prior studies have used a variety of training intervals and exercise intensities to achieve physiological benefits, in this protocol, we opted for a standardized 2-3x/week, 60 minute, 12 week regimen which is the best studied and validated training frequency and duration in which to achieve efficacy^{3, 40-43,48,78}.

Subject Retention: Utility of exercise will be emphasized to each exercise block throughout the course of the trial. If patients miss sessions, they will be immediately telephoned. A letter will be used to reach those who do not show for two or more sessions. As noted, exercise will be modified upon a patient's return from any missed sessions, but since exercise training is being administered on an intention to treat basis, the sessions will not be "made-up." Every effort will be made to foster a mutually supportive group dynamic, with the hope and intention to build expectations among the participants to support and encourage one another.

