Participants will be instructed to contact study personnel at any time if they are having any problems.

Participants who begin treatment and experience adverse outcomes sufficient to require removal from the study will receive appropriate clinical care. As in any type of treatment or clinical research program, participants’ confidentiality must be carefully guarded and respected.

All data with identifying information will be stored in locked files or password-protected computer files. Data being analyzed will be identified by subject codes, and identifying information will be removed. The identity of participants will not be revealed in the presentation or publication of any results from the project. All project staff working on the project will be educated about the importance of strictly respecting participants’ rights to confidentiality and will have completed several training courses including proper practice in accordance with HIPAA regulations, protection of human subjects, and computer security. The codes that link the names of participants and their ID numbers will be kept confidential by the PI in a secured cabinet located within his office. These data will only be accessible to the PIs and staff directly working with the study.

All personnel proposed for this project will have the required human subjects and confidentiality training, which includes information about maintaining data integrity and security. Confidentiality will be guarded using established procedures such as storing data in locked cabinets within locked offices or locked data rooms, coding by study identification numbers rather than any personally identifying information to avoid revealing the identity of subjects, and aggregating data across participants. The key linking names and study identification numbers will be kept separately from the data sets with limited access by study personnel. Only study personnel will have access to the data sets on protected servers. In order to maintain the highest standard of data entry quality, all data will be double-entered, with discrepancies highlighted so that they can be reviewed by the project coordinator. Oversight of all aspects of data management will occur with the PIs.

3. Potential Benefits of the Proposed Research to the Subjects and to Others.

The direct benefit to participants who enter this study will be to obtain the opportunity to exercise in a supervised environment.

4. Importance of the Knowledge to be gained

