In the proposed study we will use the FDA definition of adverse events (AE) and serious adverse events (SAE). Any SAE, whether or not related to study intervention, will be reported immediately to the IRB and will be followed by an additional letter detailing the nature of the SAE. In the event that a participant either withdraws from the study or the PIs decide to discontinue a participant due to a SAE, the participant will be monitored by the co-PIs until (a) a resolution is reached (e.g., the problem has resolved or stabilized with no further change expected), (b) the SAE is determined to be clearly unrelated to the study intervention, or (c) the SAE results in death. Outcomes of SAEs will be regularly reported to the VABHS IRB. A summary of the SAEs that occurred during the previous year will be included in the annual progress report as well as in the annual IRB renewal. Suicidal ideation and AEs will be formally assessed immediately after treatment and referrals for further care will be made as needed. The study will be conducted at VA Boston Healthcare System. Under the arrangement to conduct the study on site at the VA facilities, the VA agrees to provide emergency services to anyone who participates in this project. We will have specifically outlined in the Informed Consent Forms the availability of emergency services to participants who may seek them during and after normal working hours. In the Informed Consent Form, we will provide specific information about emergency contacts. Participants are instructed to contact [name] during working hours. After hours participants will be provided the information on how to contact the cardiology fellow on call. We will also provide a list of crisis hotline numbers and community resources that participants may access as well as making sure the Veterans have access to the Suicide Prevention Hotline for Veterans ([name]).

Inclusion of Women, Minorities, and Children

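### The plan does not provide for the 12-week echo after a trained patient is removed for an adverse outcome, so the intent-to-treat comparison is at risk of informative missing data

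*Combined protocol and SAP*

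**What the plan says.** **Removal.** Human Subjects 2.B (Protection Against Risk): "Participants who begin treatment and experience adverse outcomes sufficient to require removal from the study will receive appropriate clinical care". The removal is from the study, not only from training, and the sentence concerns people who have begun treatment.

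**After discontinuation.** Section 5 (Data Safety Monitoring Plan) covers a participant who withdraws. It also covers the case where "the PIs decide to discontinue a participant due to a SAE, the participant will be monitored by the co-PIs until" the event has resolved or stabilised, is judged clearly unrelated, or ends in death. Outcome assessments are not mentioned.

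**Timing of the second echo.** Under Overall Study Protocol, controls repeat the full battery 12 weeks after their first assessment. Patients in the exercise arms have an echo at baseline and another after the intervention, and Table 5 places the latter at a visit of the Merit study. For these patients, "All other parts of their participation will occur as part of the Exercise Therapy trial".

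**Analysis.** Statistical Analysis, General considerations: "Analyses will generally be performed with an intent-to-treat approach, with sensitivity analyses performed to assess the role of drop-outs on the results". No sensitivity method is named. The Aim 1 analysis uses values at baseline and at the end of follow-up, in a mixed linear model whose term of interest is time by treatment.

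**Retention.** Subject Retention applies intention to treat to missed training sessions, which are not made up. Limitations adds: "Steps will also be implemented to sustain participation in the event of illness, accidents, or travel". It does not say what these steps are.

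**The concern.** An intent-to-treat comparison needs the 12-week outcome for patients who stopped treatment as well as for those who finished. Here, stopping training because of an adverse outcome and leaving the study are described as one event, and the trained arms' follow-up echo hangs on completing the intervention and attending a visit in another study.

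Patients removed after a cardiac event or worsening heart failure are plausibly those whose volumes and ejection fraction moved the wrong way. If their second echo is not obtained, the trained arms are represented by the patients who did better. The removal sentence concerns those who begin treatment, and controls are retested by the calendar, so the loss would fall mainly on the trained arms and could make training look better against control than it is. The comparison of IMT with aerobic training could also be distorted if removals differ between those arms.

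**Working it through.** **1. Following the text for one patient.** A trained patient is removed part-way through the 12 weeks after a serious adverse event. Protection Against Risk gives clinical care, and the Data Safety Monitoring Plan gives event monitoring. The second echo is due after an intervention the patient did not complete, at a Merit visit the patient may not attend. No rule schedules it otherwise. A control with the same event still has a 12-week date. The trained patient contributes a baseline value and no change score. The mixed model keeps the record, but its time-by-treatment estimate then rests on missing at random given baseline, which is doubtful when removal follows an adverse outcome.

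**2. The plan's own figures** (Sample Size and Power; SD set to 1).
- Superiority, 30 vs 15, two-sided 5%: SE = √(1/30 + 1/15) = 0.316; noncentrality = 0.91/0.316 = 2.88 on 43 df; noncentral-t power 0.803. The detectable difference at 80% power is 0.906, so the stated 0.91 SD reproduces.
- Non-inferiority, 30 vs 30, one-sided 5%, true difference zero: SE = √(2/30) = 0.258; 0.65/0.258 = 2.52 on 58 df; power 0.800. The stated figure reproduces.

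Both use all 75 enrolled patients. There is no drop-out allowance.

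**3. Power if echoes are missing.** The loss rates are assumptions, applied equally to all arms. The only attrition figure in the documents is 5%, from an earlier large training trial (Limitations).

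| Loss | n (IMT/aerobic/control) | Superiority power at 0.91 SD | Non-inferiority power at 0.65 SD |
|---|---|---|---|
| 0% | 30/30/15 | 0.803 | 0.800 |
| 5% | 28/28/14 | 0.774 | 0.775 |
| 10% | 27/27/14 | 0.769 | 0.762 |
| 20% | 24/24/12 | 0.706 | 0.717 |

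The power cost at 5–10% is small. Bias is the larger question.

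**4. Bias against control.** Let p be the fraction of a trained arm removed without an echo, and d how much worse, in SD, their mean change would have been than that of the patients kept (mean m). The whole-arm mean is (1 − p)m + p(m − d) = m − pd, so the observed mean is too favourable by p × d. This assumes no matching loss among controls and that baseline values do not explain the difference.

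| p | d | Bias (SD) | Share of 0.91 SD | Share of 0.65 SD |
|---|---|---|---|---|
| 5% | 0.5 | 0.025 | 3% | 4% |
| 5% | 1 | 0.05 | 5% | 8% |
| 10% | 1 | 0.10 | 11% | 15% |
| 20% | 1 | 0.20 | 22% | 31% |

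**5. IMT versus aerobic.** The false non-inferiority rate at nominal one-sided 5% is 1 − Φ(1.645 ∓ pd/SE), with SE = √(1/[30(1 − p)] + 1/30). The minus sign applies if only the IMT arm loses patients, the plus sign if only the aerobic arm does. For the four rows above in order:
- loss in IMT only: 6.1%, 7.3%, 10.2%, 18.0%;
- loss in aerobic only: 4.1%, 3.3%, 2.2%, 0.9%.

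The sign of the distortion depends entirely on which arm loses more patients.

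**The case against.** The strongest reply is that this is silence, not a rule. A reader might infer that the protocol cancels the echo after removal and follows such patients only for the adverse event. No sentence says so: one passage is a human-subjects assurance and the other a safety-monitoring procedure, and neither sets out to govern outcome collection. This stands, and the point is therefore framed as an omission. It is still more than missing detail, because the trained arms' schedule, read literally, gives a removed patient no date for the echo while controls keep theirs.

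A reader might also infer that the intent-to-treat analysis cannot be delivered. That goes too far. The plan says analyses will generally be intent-to-treat, applies the principle to missed sessions, does not list missed sessions as a ground for removal, promises drop-out sensitivity analyses, and mentions steps to sustain participation in illness. A sensitivity analysis can test departures from missing at random. It cannot replace echoes that were not taken, and no method is named.

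A third tempting inference is that the non-inferiority test is anti-conservative. The protocol's remark that musculoskeletal limits hamper aerobic training would, if anything, put extra stops in the aerobic arm, which makes the test conservative. Orthopedic limitation is also an exclusion, and stopping for musculoskeletal reasons gives no ground for assuming worse cardiac change.

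Two further limits stand. The safety-monitoring text covers any participant, controls included, so the asymmetry between arms rests on the removal sentence and the visit schedule. And the Merit protocol is not available: it may keep assessing patients who stop training, so loss of the Aim 2 exercise-test and questionnaire outcomes cannot be asserted.

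**Conclusion.** The concern holds as a gap in outcome collection. Stopping training is not distinguished from leaving the study, and the 12-week echo after removal is not provided for in the trained arms. With two time points this exposes the planned analysis to informative missing data that could favour training over control.

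The size cannot be fixed from the documents, which give no removal rate; every p and d above is an assumption. At the one attrition figure quoted, the bias is small against both design differences. It becomes material only at removal rates for which the documents give no evidence. For IMT versus aerobic training, neither direction nor size can be predicted. The case for acting rests on the likely direction against control and on the low cost of the remedy, not on a demonstrated large bias in this pilot.

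**What to change.** Reconcile Protection Against Risk and the Data Safety Monitoring Plan with Overall Study Protocol, Table 5, Subject Retention and the general analysis paragraph:

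- State that stopping training, or leaving Merit, is not withdrawal from this study.
- Schedule the echo and questionnaires at 12 weeks from baseline in all three arms, unless the patient withdraws consent for assessments. Criteria for removal and decisions about exercise testing remain with the study physicians.
- Record the date and reason for stopping training separately from any withdrawal of consent.
- Include the values obtained in the intent-to-treat model. For echoes still missing, name the drop-out sensitivity analysis in advance.

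The cost is protocol and consent wording, plus a few visits by patients no longer training. The echo is non-invasive and already planned for all 75 patients. The gain will be incomplete: some patients will decline, and deaths cannot be recovered.
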